#### 7.1.3 Contraception and pregnancy

Not applicable.

## 7.2 Definitions

### 7.2.1 Adverse event

An AE is defined as any untoward medical occurrence in a patient or clinical investigational patient administered a pharmaceutical product that does not necessarily

have a causal relationship with study-drug treatment. An AE can therefore be any unfavourable and unintended sign (for example, including an abnormal laboratory finding), symptom, or disease temporally associated with the use of a medicinal product, whether or not considered related to the medicinal product. Complications associated with scheduled procedures are considered AEs.

Events that occur following the full execution of the ICF but prior to dosing are discussed in Section [7.4.2](#).

Adverse events will be coded using the standard Medical Dictionary for Regulatory Activities (MedDRA), and grouped by System Organ Class and Preferred Term.

### 7.2.2 Serious adverse event

An SAE is any AE that meets 1 or more of the following criteria:

- Results in death
- Is life-threatening
- Requires inpatient hospitalisation, or prolongation of existing hospitalisation
- Results in persistent or significant disability/incapacity
- Is a congenital anomaly/birth defect
- Is classified as an important medical event or medically significant event

Medical and scientific judgement should be exercised in deciding whether an AE should be considered an important medical event (and consequently an SAE). Such events may not be immediately life-threatening or result in death or hospitalisation, but may jeopardise the patient, or may require intervention to prevent one of the outcomes listed in the definitions above. These situations should also usually be considered serious.

It should be noted that:

- Death is considered an outcome of an AE. Whenever possible the underlying cause of death must be reported as the AE.
- A life-threatening SAE is any adverse experience that places the patient at risk of death at the time of its occurrence, i.e., it does not include a reaction that, had it occurred in a more severe form, might have caused death.
- Inpatient hospitalisation is defined as any inpatient admission, even if for less than 24 hours. For chronic or long-term inpatients, inpatient admission also includes transfer within the hospital to an acute/intensive care inpatient unit.

The following hospitalisations, whether planned before or during the study, should not be considered and reported as SAEs:

- Routine treatment not associated with any deterioration in condition
- Elective or planned treatment, including surgical interventions, both related and unrelated to the patient's LOS, if the plan for the respective intervention was documented prior to the first dose of study drug
- Elective or pre-planned treatment for a pre-existing condition that is unrelated to the patient's LOS and has not worsened
- Admission to a hospital or other institution for general care, not associated with any deterioration in condition

### 7.2.3 Adverse drug reaction

In the context of this study protocol, an ADR or serious adverse reaction (SAR) is an AE or SAE respectively for which there is a reasonable possibility that the drug caused the event, i.e., it has been assessed by the Investigator and/or the Sponsor as either *Possibly related* or *Probably related* to the study drug or to ampicillin or an aminoglycoside (see Section 7.3.2).

### 7.2.4 Suspected unexpected serious adverse reaction

A suspected unexpected serious adverse reaction (SUSAR) is any SAE considered by the Investigator or by the Sponsor to be *Possibly related* or *Probably related* to the study drug or to ampicillin or an aminoglycoside (see Section 7.3.2), which is not listed in the Reference Safety Information applicable at the time of occurrence of the event, or is not listed at the specificity (i.e., nature, outcome) or severity that has been observed.

### 7.2.5 Adverse events of special interest

An adverse event of special interest (AESI) is defined as a serious or non-serious AE that is of scientific and medical concern specific to the sponsor's product for which ongoing monitoring and rapid communication by the investigator to the sponsor can be appropriate. The following are considered AEs of special interest for the purposes of this study, based on nonclinical data and the known safety profile of ceftobiprole or the cephalosporin class of antibiotics, and are to be promptly reported in the eCRF, along with an assessment of relationship by the Investigator:

- Hypersensitivity reactions
- Convulsions
- *Clostridioides difficile*-associated colitis or pseudomembranous colitis
- Hepatic enzyme increased
- Hyponatremia
- Renal failure
- Infusion site reactions
- Thromboembolic events

### 7.2.6 Further adverse event definitions

Wherever possible, a specific disease or syndrome rather than individual associated signs and symptoms should be identified. However, if an observed or reported sign or symptom is not considered by the Investigator to be a component of a specific disease or syndrome, it should be recorded as a separate AE.

Laboratory data are to be collected as stipulated in Section 5.5.4. Clinical syndromes associated with laboratory abnormalities are to be recorded as appropriate (e.g., diabetes mellitus instead of hyperglycemia).

### 7.2.7 Special Situations

Special Situations include overdose, misuse, and medication error. A Special Situation may occur with or without an associated AE.

- **Overdose:** Administration of a quantity of a medicinal product once or cumulatively which is above the maximum recommended dose indicated in the authorized product information or administration specification set out in this protocol. Clinical judgement should always be applied when applying this definition.
- **Misuse of a medicinal product:** Intentional and inappropriate use of a medicinal product not in accordance with the terms indicated in the authorized product information or administration specification set out in this protocol.
- **Medication error:** An unintended failure in the drug treatment process that leads to, or has the potential to lead to, harm to the patient.

## 7.3 Evaluation of adverse events

### 7.3.1 Grading of severity

The severity of an AE will be graded on the following scale:

- Mild: no change in baseline age appropriate behaviour\*
- Moderate: resulting in minor changes of baseline age-appropriate behaviour
- Severe: resulting in major changes of baseline age-appropriate behaviour\* and/or non-life threatening changes in basal physiological processes\*\*
- Life-threatening
- Fatal

\* Age-appropriate behaviour refers to oral feeding behaviour, voluntary movements and activity, crying pattern, social interactions and perception of pain

\*\* Basal physiological processes refer to oxygenation, ventilation, tissue perfusion, metabolic stability and organ functioning

### 7.3.2 Assessment of causality

The relationship between an AE and the study drug will be determined by the Investigator on the basis of their clinical judgement and the following definitions.

To align with the binary causality assessment required for clinical studies, based on the Investigator's evaluations, the cases will be categorised as:

- Unrelated: when evaluated as *Unlikely related* or *Not related* to the study drug or to ampicillin or an aminoglycoside
- Related: when evaluated as *Probably related* or *Possibly related* to the study drug or to ampicillin or an aminoglycoside

## UNRELATED

This category comprises events that are either

- ***Not related*** to the study drug or to ampicillin or an aminoglycoside, i.e., clearly and incontrovertibly due only to extraneous causes such as the patient's clinical state, environmental or toxic factors, or other modes of therapy administered to the patient, or
- ***Unlikely related*** to the study drug or to ampicillin or an aminoglycoside, i.e., the event may readily have been produced by the patient's clinical state, environmental or toxic factors, or other modes of therapy administered to the patient

An AE is also categorised as *Unlikely related / Not related* if it does not follow a reasonable temporal sequence from administration of the study drug or ampicillin and/or an aminoglycoside, i.e., based on the time between the administration of study drug and occurrence of the event, a relationship is not plausible.

Examples for the absence of a reasonable temporal sequence from administration of the study drug are that the drug was:

- Re-administered, and the event did not recur, or
- Interrupted or stopped, and the event did not improve or disappear

Finally, an AE may be assessed to be *Not related / Unlikely related* if it does not follow a known pattern of the response to the study drug or drugs of the same substance class.

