#### ***Possibly related***

An AE may be considered to be (at least) *Possibly related* to the study drug or treatment with ampicillin and/or an aminoglycoside if:

- It follows a reasonable temporal sequence from administration of the study drug or ampicillin and/or an aminoglycoside (see also additional explanations above), or it follows a known pattern of the response to the suspected drug or drugs of the same substance class; or
- It may or may not have been produced by the patient's clinical state, environmental or toxic factors, or other modes of therapy administered to the patient; or
- It does not follow a plausible temporal relationship or a known pattern of response but there is no alternative explanation for the event.

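### Protocol 7.3.2 counts non-recovery after stopping the drug as lack of a plausible time sequence, so an irreversible or fatal AE with plausible onset can be classed Unrelated

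*Protocol*

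**What the plan says.** Protocol 7.3.2 has the Investigator decide causality "on the basis of their clinical judgement and the following definitions". The definitions then pull in different directions.

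**Unrelated.** The temporal rule opens with "An AE is also categorised as" Unlikely or Not related, and applies when there is no reasonable temporal sequence. It explains this as meaning that "based on the time between the administration of study drug and occurrence of the event, a relationship is not plausible". Two examples of an absent sequence follow. One is a negative rechallenge. The other is that the drug was "Interrupted or stopped, and the event did not improve or disappear". A closing sentence begins "Finally, an AE may be assessed to be" Not or Unlikely related, and applies "if it does not follow a known pattern of the response to the study drug or drugs of the same substance class".

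**Probably related.** Any one of three criteria is enough: plausible timing, a known pattern, or no other reasonable explanation. The verb is permissive.

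**Possibly related.** Also permissive. Plausible timing alone or a known pattern alone is enough, and so is an event that might or might not come from the patient's clinical state. The last option reads: "It does not follow a plausible temporal relationship or a known pattern of response but there is no alternative explanation for the event".

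The protocol does not say which category prevails when an event meets criteria in both.

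**The concern.** Recovery after stopping a drug is evidence for a causal link only when the effect is reversible. Failure to recover says little about a lasting effect and nothing about when the event began. The protocol itself expects some events to be irreversible: Section 7.4.4 provides for following unresolved events until they are deemed so, death included. Section 7.2.5 lists events of special interest that may leave lasting damage, among them renal failure and "Thromboembolic events".

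The call has consequences:

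- SAP 9.1, 9.1.1 and 9.1.2 build the study-drug-related AE, SAE and AESI summaries on it.
- Protocol 7.2.3 and 7.2.4 use it for ADR, SAR and SUSAR status.
- Protocol 7.4.4 continues follow-up beyond LFU for unresolved ADRs, SARs and unrelated SAEs. A non-serious AE classed Unrelated because it persisted therefore drops out of follow-up at LFU.
- Protocol 7.4.5 collects only SARs after LFU.
- Protocol 5.6.1 counts discontinuation with a need for non-study antibacterials as clinical failure when the reason is a treatment-related AE. If the AE is classed Unrelated, that criterion is not met.

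**Working it through.** The plan gives no figure on this point, so there is none to reproduce. The check is to run types of event through the 7.3.2 criteria as written.

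| Event | Unrelated text | Related text | Result |
|---|---|---|---|
| A. Onset during treatment, drug stopped, no improvement, known pattern | Meets the non-recovery example (categorical) | Probably or Possibly, by timing or by pattern (permissive) | Both met |
| B. Plausible onset, fatal despite stopping | Meets the non-recovery example (categorical) | Probably or Possibly, by timing (permissive) | Both met |
| C. Plausible onset, unfamiliar pattern, resolves on stopping | Known-pattern sentence (permissive) | Probably or Possibly, by timing (permissive) | Both met |
| D. Neither plausible timing nor known pattern, no alternative explanation | Temporal rule (categorical) | Possibly, last option (permissive) | Both met |
| E. Onset during treatment, improving but unresolved at LFU | Non-recovery example not met | Probably or Possibly, by timing | No conflict |
| F. Onset after the last dose | No natural reading of the non-recovery example | Judged on the remaining criteria | No conflict from the example |

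1. In A and B the timing is plausible under the protocol's own explanation, so the temporal rule should not apply. It is brought in only by the example. The example contradicts the definition it illustrates.
2. In A, B and D a categorical rule meets permissive ones. With no precedence stated, a literal reader could let the categorical rule win. Two Investigators could classify the same event differently, and both would be following the text.
3. In C both sides are permissive. This is an overlap without a tie-breaker, not a flat contradiction.
4. The last Possibly related option requires that there be no alternative explanation. That may be hard to satisfy in septic neonates who may also be receiving ampicillin or an aminoglycoside.

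**Scale, for illustration only.** Protocol 8.3 and SAP 4.1 plan eight patients, six pre-term and two term. The table shows the effect of moving one patient between related and unrelated. The intervals are exact (Clopper-Pearson) 95% intervals, which the SAP does not plan. For 0 of n the upper limit is 1 − 0.025^(1/n); with n = 8 this is 1 − 0.025^(1/8) = 36.9%. For 1 of n the limits are the 2.5% point of Beta(1, n) and the 97.5% point of Beta(2, n − 1).

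| Group | 0 related | 1 related |
|---|---|---|
| All (8) | 0% (0 to 36.9%) | 1/8 = 12.5% (0.3 to 52.7%) |
| Pre-term (6) | 0% (0 to 45.9%) | 1/6 = 16.7% (0.4 to 64.1%) |
| Term (2) | 0% (0 to 84.2%) | 1/2 = 50% (1.3 to 98.7%) |

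Any change of one patient at these sample sizes gives these figures. They do not estimate how often the wording would alter a call.

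**The case against.** The strongest defence is that causality is a clinical judgement with several routes to Related. Renal failure, convulsions and thromboembolic events are on the AESI list because of nonclinical data or the known profile of the drug or its class, so they can be argued to follow a known pattern, and that alone permits Probably related. New harms can be called Possibly related on timing alone. The Sponsor can also judge an event related (Protocol 7.2.3 and 7.2.4). SAEs go to the Sponsor within 24 hours whatever their causality (7.4.3.2.1), AESIs are identified by MedDRA query or term (SAP 9.1.4), and all AEs are listed.

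These points stand, and they rule out three stronger readings that a reader might infer:

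- *Every AE still open at LFU falls under the rule.* It does not. The example needs an event that has not improved, so an improving event is outside it, and an event that starts after the last dose is not a natural case for it.
- *New kinds of harm must be called Unrelated.* The known-pattern sentence only permits that call, and the Possibly related text permits the opposite one.
- *The primary safety result is distorted.* The primary endpoint (Protocol 3.2.1, SAP 3.2.1) has no relatedness condition, and SAP 9.1.1 tabulates all AEs regardless of causality.

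The defence does not remove the core problem. Judgement is to be exercised together with the definitions, and one definition carries an example that contradicts it under categorical wording. The routes to Related are all permissive and nothing says that they prevail.

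**Conclusion.** The wording is wrong as written and can produce a wrong causality call. It does not follow that it will. The events exposed are those with plausible onset that fail to improve after the drug is stopped, including irreversible and fatal ones. Events of unfamiliar pattern are also exposed, less strongly, through the permissive sentence.

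The effect is confined to the study-drug-related AE, SAE and AESI summaries, Investigator-assigned ADR, SAR and SUSAR status, follow-up and collection after LFU, and the clinical-failure criterion based on a treatment-related AE. Even there, cure still requires that no further antibacterial therapy is needed, so the direct effect is on who meets that failure criterion.

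The frequency cannot be estimated from the documents. The conclusion assumes that Investigators apply the text as written. Where they follow the onset-based explanation and ignore the example, the problem does not arise.

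**What to change.** In the Unrelated text of Protocol 7.3.2:

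1. Delete the example of an event that persists after the drug is interrupted or stopped.
2. State that neither a negative dechallenge nor an unfamiliar pattern, on its own, makes an AE unrelated when onset plausibly followed dosing.
3. State that where an event meets criteria in both sets, the Probably or Possibly related criteria take precedence.

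Align the eCRF completion guidelines if they repeat the current wording. The cost is a wording amendment and possibly a few more events classed as related. Visits, sample size and analysis methods do not change.

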## RELATED

### *Probably related*

This category is applicable to an AE that is considered, with a high degree of certainty, to be related to the study drug or to ampicillin and/or an aminoglycoside (i.e., this category also comprises events that are definitely related to the study drug).

An AE event may be considered (at least) *Probably related* (or considered definitely related) to the study drug or ampicillin and/or an aminoglycoside if it meets one or more of the following criteria:

- It follows a reasonable temporal sequence from administration of the study drug or ampicillin and/or an aminoglycoside, i.e., based on the time between the administration of study drug and the occurrence of the event, a relationship is plausible, e.g.,
  - The drug was interrupted or stopped, and the event improved or disappeared
  - The drug was re-administered, and the event recurred

- It follows a known pattern of the response to the suspected drug or drugs of the same substance class
- It cannot be reasonably explained by the known characteristics of the patient's clinical state, environmental or toxic factors, or other modes of therapy administered to the patient

#### ***Possibly related***

An AE may be considered to be (at least) *Possibly related* to the study drug or treatment with ampicillin and/or an aminoglycoside if:

- It follows a reasonable temporal sequence from administration of the study drug or ampicillin and/or an aminoglycoside (see also additional explanations above), or it follows a known pattern of the response to the suspected drug or drugs of the same substance class; or
- It may or may not have been produced by the patient's clinical state, environmental or toxic factors, or other modes of therapy administered to the patient; or
- It does not follow a plausible temporal relationship or a known pattern of response but there is no alternative explanation for the event.

### **7.4 Handling of safety information and collection periods**

#### **7.4.1 Responsibilities and procedures**

The responsibility for the safety of an individual patient lies in all cases with the Investigator. This includes the timely review of all safety data obtained during the course of the study.

An Investigator must instruct the parent(s) or LAR to report any AEs the patient experiences.

#### **7.4.2 Handling of safety data during the pre-treatment period**

Any relevant change in, or worsening of, a patient's condition occurring after execution of the study ICF but prior to dosing, is to be recorded in the medical history page of the eCRF (see Section 5.3.1), unless the occurrence is assessed as related to the study procedure, in which case it must be recorded in the AE page. If the event is assessed as both serious (see Section 7.2.2) and related to study-specific procedures, it must be reported to the Sponsor's safety representative, using the same procedures as for an SAE (see Section 7.4.3.2).

#### **7.4.3 Handling of safety data during the treatment period and up to the last scheduled follow-up**

From the start of first dosing up to and including the LFU visit 28–35 days after the last study drug administration, any change in, or worsening of, a patient's condition, all AEs, and Special Situations must be collected and reported in the eCRF (See Section 9.1.2). SAEs must in addition be reported and recorded on the SAE form (see Section 7.4.3.2).

#### 7.4.3.1 Reporting procedures for adverse events that do not meet seriousness criteria

All AEs directly observed (physical examination, laboratory test, or other assessments), mentioned by the parent(s) or LAR, or reported by the parent(s) or LAR upon non-directive questioning, must be recorded on the AE pages of the eCRF in the English language, and should include the following information:

- The term identifying the event. If possible, a diagnosis should be documented rather than signs and symptoms, using self-explanatory and concise medical terminology. If an observed or reported sign or symptom is not considered a component of a specific disease or syndrome by the Investigator, it should be recorded as a separate AE. Note that disease progression is considered an efficacy outcome parameter, and should not be recorded as an AE unless the outcome is death.
- Duration (start and end dates)
- Grading of severity (see Section [7.2.3](#))
- Relationship to study drug (causality assessment) (see Section [7.3.2](#))
- Action taken in regard to study drug or ampicillin and/or an aminoglycoside or any suspected concomitant medication
- Additional treatments given for the event
- Whether the event is an SAE (seriousness assessment) (see Section [7.2.2](#))
- Outcome

Further details on completing the relevant pages in the eCRF are provided in the eCRF completion guidelines. In addition, concomitant medications (with start and stop dates) and medical history should be updated as needed.

Abnormal laboratory results should not be recorded as an AE unless the abnormal result meets 1 or more of the following criteria:

- Induces clinical signs or symptoms which require therapy or additional diagnostic evaluation
- Requires study drug dose modification or discontinuation
- Is considered clinically significant

If a laboratory abnormality meets 1 of the above criteria, the clinical syndrome associated with the laboratory abnormality is to be recorded (e.g., diabetes mellitus instead of hyperglycemia).

Adverse events must also be reported in the source document with at least the nature of the event, the start and end date, the relationship to study drug, treatment (if applicable), and outcome (in the initial or follow-up report).

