#### 9.1.4 Adverse events of special interest

Adverse events of special interest (AESI) are defined in protocol Section 7.2.5 as hypersensitivity reactions, convulsions, *clostridioides difficile*-associated colitis or pseudomembranous colitis, hepatic enzyme increased, hyponatremia, renal failure, infusion site reactions, and thromboembolic events. These AESIs will be identified using the following narrow Standardized MedDRA Query (SMQ) or MedDRA PTs:

- Hypersensitivity reactions (Narrow SMQ code 20000214)
- Convulsions (Narrow SMQ code 20000079)
- *Clostridioides (Clostridium) difficile*-related AEs (Narrow SMQ code 20000080)
- Hepatic enzyme increased (PTs: Hepatic function abnormal, Alanine aminotransferase, Alanine aminotransferase abnormal, Alanine aminotransferase increased, Aspartate aminotransferase abnormal, Aspartate aminotransferase increased, Hepatic enzyme abnormal, Hepatic enzyme increased, Liver function test abnormal, Liver function test increased, Transaminases increased)
- Hyponatremia (PTs: Blood sodium decreased or Hyponatraemia)
- Acute renal failure (Narrow SMQ code 20000003)
- Extravasation events (injections, infusions and implants) (Broad SMQ code 20000136)
- Embolic and thrombotic events (Narrow SMQ code 20000081).

Adverse events of special interest will be summarized by SOC and PT.

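### A hepatic enzyme rise recorded as a liver diagnosis, as Protocol 7.4.3.1 directs, is missed by the term list that SAP 9.1.4 uses for the hepatic AESI

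*Protocol*

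**What the plan says.** Protocol Section 7.2.5 lists eight AESIs. Two of them, hepatic enzyme increased and hyponatremia, are laboratory findings. AESIs "are to be promptly reported in the eCRF, along with an assessment of relationship by the Investigator". The section defines an AESI as a kind of AE and sets no laboratory threshold.

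Protocol Section 7.4.3.1 governs when a laboratory result becomes an AE: "Abnormal laboratory results should not be recorded as an AE unless the abnormal result meets 1 or more of the following criteria". The three alternatives are:
- "Induces clinical signs or symptoms which require therapy or additional diagnostic evaluation"
- "Requires study drug dose modification or discontinuation"
- "Is considered clinically significant"

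When one is met, "the clinical syndrome associated with the laboratory abnormality is to be recorded (e.g., diabetes mellitus instead of hyperglycemia". Section 7.2.6 gives the same rule more loosely: "Clinical syndromes associated with laboratory abnormalities are to be recorded as appropriate". Neither section mentions AESIs.

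SAP Section 9.1.4 identifies AESIs from coded AE terms. Six of the eight use a Standardized MedDRA Query. The two laboratory AESIs use fixed lists of preferred terms (PTs): 11 enzyme or liver-function terms for the hepatic AESI, and two for sodium, "Hyponatremia (PTs: Blood sodium decreased or Hyponatraemia". SAP Section 9.1 adds overview lines for AESIs and for study-drug-related AESIs.

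**The concern.** The recording rule and the search rule pull apart for the hepatic AESI. The site is told to write down the diagnosis, and the example in 7.4.3.1 puts the diagnosis in place of the laboratory term rather than beside it. The SAP then searches only for the laboratory term. An infant whose enzyme rise has developed into a named liver disorder can be absent from the table meant to show hepatic events, while an infant with an isolated enzyme rise is present.

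At stake are the hepatic AESI count, the AESI line of the AE overview (unless the infant has another AESI) and the study-drug-related AESI line. The last of these matters because the laboratory tables carry no causality assessment. Two sites could also report the same infant differently, depending on how each reads 7.2.5 against 7.4.3.1.

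**Working it through.** The plan gives no figure to reproduce: the sample size has no power basis (Protocol 8.3, SAP 4.1) and no AESI rate is assumed. The check is to follow cases through the two rules.

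| Case | Recorded under Protocol 7.4.3.1 as | Counted by SAP 9.1.4? |
|---|---|---|
| A. Enzyme rise meeting none of the three criteria | Not an AE | No; consistent with 7.2.5, since an AESI must first be an AE |
| B. Isolated enzyme rise meeting a criterion | Enzyme term | Yes |
| C. Enzyme rise meeting a criterion, part of a diagnosed liver disorder | The diagnosis | Not as the hepatic AESI, unless it codes to a listed term such as Hepatic function abnormal |
| D. Low sodium meeting a criterion, reported as hyponatraemia | Hyponatraemia | Yes |
| E. Low sodium meeting a criterion, replaced by another syndrome | That syndrome | Not as hyponatremia |

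Case C is the defect. Case E is possible, but the documents name no syndrome that would replace the term.

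**Size per infant.** Planned numbers are 8 in all, 6 pre-term and 2 term:
- overall 1/8 = 12.5 percentage points
- pre-term 1/6 = 16.7 points
- term 1/2 = 50 points

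For example, with one infant in case B and one in case C, the table shows 1/8 = 12.5% where 2/8 = 25.0% had a qualifying enzyme rise.

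**Chance that the table shows any event.** This is illustration only. Let p be the true proportion of infants with a qualifying event and c the fraction recorded under a listed term. Neither is in the documents. With n = 8, the chance of at least one counted infant is 1 − (1 − p·c)^8.

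| p | c = 1 | c = 0.75 | c = 0.5 |
|---|---|---|---|
| 5% | 33.7% | 26.3% | 18.3% |
| 10% | 57.0% | 46.4% | 33.7% |
| 20% | 83.2% | 72.8% | 57.0% |
| 30% | 94.2% | 87.0% | 72.8% |

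At p = 10% and c = 0.5, for instance, 1 − 0.95^8 = 33.7%, against 1 − 0.90^8 = 57.0% with full capture.

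**The case against.** The strongest reply is that nothing is lost from the report as a whole. A liver diagnosis still appears in the tables by System Organ Class and PT (SAP 9.1.1) and in the AE listing. The enzyme values appear in the change-from-baseline summaries, the shift tables against minimum and maximum post-baseline values, and a listing that flags out-of-range results (SAP 9.3). With eight infants, a reader can go through the listings case by case. Section 7.2.6 leaves room for judgement, and the eCRF completion guidelines cited in 7.4.3.1, which are not among the documents, may already settle the matter. All of this stands, and it confines the loss to the AESI outputs. It does not repair them. ALT, AST and sodium are mandatory only at Screening and the end-of-treatment visit (Protocol Table 4), so the laboratory tables are also a limited backstop.

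A reader might infer more than the documents support:
- **That 7.2.5 and 7.4.3.1 contradict each other, so a rise judged not clinically significant is a lost AESI.** An AESI is defined as an AE, so the sections can be read in sequence. There are also three routes to becoming an AE, not one.
- **That hyponatremia is counted less as it becomes more overt.** Hyponatraemia is a listed PT, so symptomatic low sodium reported under that name is counted.
- **That the primary endpoint itself is miscounted.** Protocol 8.1.1 does not name AESIs. The diagnosis enters it as an AE and the enzyme values as laboratory tests.

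**Conclusion.** The point holds for the hepatic AESI. Following Protocol 7.4.3.1 and SAP 9.1.4 as written, an enzyme rise recorded only as a liver diagnosis outside the 11 listed terms is left out of the hepatic AESI count and its drug-related subset. For hyponatremia the same gap is conditional on another syndrome replacing the term.

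Under-recording is a risk, not an established fact. It requires that such a case occurs, that the site substitutes the diagnosis rather than adding it, and that the completion guidelines do not say otherwise. If it happens, each missed infant costs 12.5 percentage points overall, 16.7 among pre-term and 50 among term infants at the planned numbers. The effect is on one category of a descriptive safety report whose listings still hold the information. The correction is cheap enough to be worth making.

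**What to change.** 1. **Protocol 7.4.3.1 and 7.2.6, or the eCRF completion guidelines.** Reconcile these with 7.2.5 and SAP 9.1.4 by stating that a hepatic enzyme increase or hyponatremia that is worse than baseline and meets a 7.4.3.1 criterion is recorded under its own term in addition to any syndrome. The worse-than-baseline condition is needed because exclusion criterion 8 admits infants with ALT or AST up to 8 times the age-specific upper limit; without it, pre-existing elevations could become AESIs.
2. **SAP 9.1.4.** Also count hepatic diagnosis terms towards the hepatic AESI where the infant's ALT or AST rose from baseline.
3. **SAP 9.1.4 or 9.3.** Add one cross-check line or listing, kept separate from the AESI count, of infants with post-baseline ALT or AST above the laboratory range, or sodium below it, worse than baseline, and with no matching AESI.

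Items 2 and 3 use data already collected and help even if site recording can no longer be changed. No new test is needed. The costs are a sentence in the protocol or guidelines, a few SAP lines, a few more AE records, possible double entry of one event, and a slightly higher AESI count.
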